	Incidence rate of atrial fibrillation (AF)
	Tertiary endpoints: 1) Change in functional class (NYHA). 2) Safety
	endpoints (incidence rate of Major hypoglycemia, Symptomatic hypotension,
	Genito-urinary infections, Ketoacidosis, Amputation, and Necrotizing Fasciitis
	of the Perineum (Fournier's Gangrene). 3) Crossovers.
Population	Patients with aortic stenosis and prior history of HF or reduced LVEF
	discharged after TAVI.
Inclusion criteria	• ≥18 years old.
	Severe aortic stenosis underwent TAVI.
	Prior heart failure admission and one of the following criteria:
	➤ Left ventricular ejection fraction ≤ 40% or
	Diabetes mellitus or
	➤ Estimated glomerular filtrate rate 25-75 ml/min/1.73 m2
Exclusion criteria	Known allergy or intolerance to SGLT2 inhibitors.
	Concomitant therapy with sulfonylurea or SGLT2 inhibitors.
	• Systolic blood pressure < 100 mmHg or diastolic blood pressure < 50
	mmHg.
	An estimated glomerular filtration rate (GFR) below 25 ml per
	- , , , -

[figure not shown]

	minute per 1.73 m2.
	_
	Chronic cystitis and/or recurrent urinary tract infections (2 or more in
	the last year)
	Poor control of diabetes mellitus that requires SGLT-2 inhibitor
	prescription on discharge according to treating physician judge.
	Any medical condition that, in the investigator's judgment, would
	seriously limit life expectancy (less than one year).
	Pregnant or breast-feeding patients
	Patients participating in other clinical trials.
Phase	IV.
Number of Sites	26.
Study Drug	Dapagliflozin 10-mg daily dose.
Comparator	Control (no dapagliflozin).
Power calculation	- Anticipated effect size: dapagliflozin treatment will be associated with a 30%
	reduction in the incidence rate of the primary composite endpoint
	Anticipated incidence control arm: 30%
	Anticipated incidence in dapagliflozin arm: 21%
	- Power: 0.8
	- Anticipated incidence of withdrawals/losses in follow-up: 5%
	- Sample size (including withdrawals): 1,020 (510 per treatment arm)
Events	Events will be adjudicated by a blinded committee after reviewing information
adjudication	sent by local investigators
Interim analyses	Two interim analyses will be performed on primary endpoint and secondary
	safety endpoints when 33% and 66% of events have been adjudicated (81 and
	172 events respectively).
Chronogram	2021-2024
	Q1 2021: Start of inclusion
	Q1 2022: Half way with inclusion (510 patients)
	Q1 2023: Anticipated end of inclusion (1,020 patients)
	Q1 2024: End of follow-up

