 Dapagliflozin therapy in TAVI patients with prior history of HF and diabetes mellitus, reduced LVEF (LVEF ≤ 40%) or renal dysfunction (eGFR 25-75 ml/min/1.73 m2), is associated with reduced 1-year mortality or worsening of HF.

Secondary hypotheses:

- 1) Dapagliflozin therapy in TAVI patients with prior history of HF and diabetes mellitus, reduced LVEF (LVEF ≤ 40%) or renal dysfunction (eGFR 25-75 ml/min/1.73 m2), is associated with reduced 1-year CV mortality
- 2) Dapagliflozin therapy in TAVI patients with prior history of HF and diabetes mellitus, reduced LVEF (LVEF ≤ 40%) or renal dysfunction (eGFR 25-75 ml/min/1.73 m2), is associated with reduced 1-year incidence of AF.
- 3) Dapagliflozin therapy in TAVI patients with prior history of HF and diabetes mellitus, reduced LVEF (LVEF ≤ 40%) or renal dysfunction (eGFR 25-75 ml/min/1.73 m2), is associated with improvement in functional class.

STUDY DESIGN AND ENDPOINTS

DESCRIPTION OF THE STUDY DESIGN

Dapa-TAVI is a pragmatic, controlled, prospective, randomized, open-label blinded endpoint (PROBE design) clinical trial. Patients being discharged after TAVI who meet all inclusion criteria, and none of the exclusion criteria, will be eligible for the enrollment. Patients will be 1:1 randomized to 1 of these 2 arms:

- **Intervention group:** Sodium-glucose cotransporter-2 (SGLT-2) inhibitor therapy with daily oral dose of dapagliflozin 10 mg.
- **Control group:** no SGLT-2 inhibitor therapy with dapagliflozin.

Apart from dapagliflozin therapy (or control), patients will be treated according to current standards (per managing physician prescription).

STUDY ENDPOINTS

> PRIMARY ENDPOINT

• Incidence rate of the composite of all-cause mortality or worsening HF (including hospitalization for HF or an urgent visit resulting in intravenous therapy for HF).

> SECONDARY ENDPOINTS

- Indicence rate of individual components of primary endpoint.
- Incidence rate of CV death.
- Incidence rate of atrial fibrillation (AF).

> TERTIARY ENDPOINTS

- Improvement in NYHA class.
- Safety endpoints:
 - Symptomatic hypotension. Symptomatic hypotension includes postural dizziness with systolic blood pressure < 100 mmHg, and orthostatic hypotension (defined as a decrease of >20 mmHg in systolic blood

- pressure or >10 mmHg in diastolic blood pressure from a supine to a standing position).

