- Major hypoglycemia. Major hypoglycemia is defined as an event where all the following criteria were confirmed by the investigator: (1) the patient experienced symptoms of severe impairment in consciousness or behaviour; (2) the patient needed external assistance; (3) intervention was needed to treat the hypoglycaemia; and (4) there was prompt recovery of acute symptoms following the intervention.
- Ketoacidosis.
- Genital or Urinary Infections
- Amputation
- Necrotizing Fasciitis of the Perineum (Fournier's Gangrene)
- Crossovers (incidence rate and reasons).

[figure not shown]
STUDY ENROLLMENT AND WITHDRAWAL

Estimated date to initiate enrollment is Q1 2021. It is anticipated that enrollment will be performed in a 2 years time frame. Screening of patient candidates will be done during index hospital admission (i.e. admission for TAVI). Individuals meeting inclusion criteria (and not meeting any exclusion criterion) will be invited to participate immediately before hospital discharge. Patients may be recruited after hospital discharge as long as randomization is one within two following weeks after TAVI.

Women and members of minority groups and their subpopulations will be included in accordance with the NIH (National Institutes of Health) Policy on Inclusion of Women and Minorities as Participants In Research Involving Human Subjects.

Anticipated recruitment rate.

Anticipated cumulative recruitment

PARTICIPANT INCLUSION CRITERIA

- Patients (≥18 years, both genders) with severe aortic stenosis (aortic valve area ≤ 1.0 cm2, or indexed aortic valve area ≤ 0.6 cm2/m2, or jet velocity ≥ 4.0 m/s, or mean gradient ≥ 40 mmHg) underwent TAVI.
- ➤ Prior heart failure admission and one of the following criteria:
 - Left ventricular ejection fraction $\leq 40\%$ or
 - o Diabetes mellitus or
 - o Estimated glomerular filtrate rate 25-75 ml/min/1.73 m2

PARTICIPANT EXCLUSION CRITERIA

An individual who meets any of the following criteria will be excluded from participation in this study:

- 1) Known allergy or intolerance to SGLT2 inhibitors.
- 2) Concomitant therapy with sulfonylurea or SGLT2 inhibitors.
- 3) Systolic blood pressure < 100 mmHg or diastolic blood pressure < 50 mmHg.
- 4) An estimated glomerular filtration rate (GFR) below 25 ml per minute per 1.73 m2.
- 5) Chronic cystitis and/or recurrent urinary tract infections (2 or more in the last year)

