Once a potential event is detected either by a local investigator or during a follow-up, a report from the hospital in which the patient is admitted will be requested (with any personal identification of the patient blinded). All events need to be adjudicated by the Clinical Events Adjudication Committee (CEAC). For the evaluation of the events, the local investigator should prepare anonymous copies of the original source of data (clinical reports, complementary tests [catheterizations, ECG, X-ray, etc], lab tests and all relevant information). The regional PI will be responsible for sending the information confidential to the scientific project manager, who will prepare documentation for the CEAC. The CEAC will have a chairman and 3 additional

members. All events will be evaluated by at least 2 members of the CEAC. In the case of controversies, the opinion of the chairman will prevail.

Patients will be followed up for the entire duration of the study regardless of having an adjudicated event. For the composite primary endpoint, the first event will be included in analysis, but for secondary endpoints, different events in the same patients will be individually evaluated.

CENTERS SELECTION

Any center with TAVI program is eligible to participate. During hospital selection, the number of patients discharged with a TAVI during the past 12 months will be evaluated. A minimum number of patients per year (n=12) will be agreed with the hospital. Hospitals not fulfilling the agreed number will eventually be disqualified from recruitment. Hospital with electronic medical records will be prioritized.

RANDOMIZATION AND STRATEGIES FOR RECRUITMENT

Patients will be screened during index hospitalization for TAVI. At discharge (or after discharge provided randomization takes place within 14 days after TAVI), and after informed consent is signed, patients will be randomized to receive or not dapagliflozin. After discharge, patients will be included in each center's TAVI follow-up program (as per local practice).

Randomization will be done via web or via a dedicated mobile application. Each investigator participating in the trial will have a log-in username and password that links her/him to a specific hospital. During randomization, ten fields will be needed to complete:

- 1. Full name of patient
- 2. Telephones (personal and that from relatives)
- 3. Date of TAVI
- 4. DM status.
- 5. Age
- 6. Sex
- 7. Creatinine (mg/dL)
- 8. LVEF (%).

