- ACQUISITION OF STUDY MEDICATION: This is a pragmatic trial and dapagliflozin therapy is included in the clinical practice armamentarium. Thus, prescription of dapagliflozin agent will be done by physicians according to randomization arm. The study will not provide with any medication to the study.
- DURATION OF THERAPY: The patient will be maintained with / without dapagliflozin throughout the study period (1 year) if no crossover occurs (see specific section).

MANAGEMENT OF PATIENTS AFTER A THE OCCURRENCE OF AN EVENT

When a patient suffers a clinical event (included or not in the list of clinical endpoints), treating physicians are encouraged to contact the coordinating center and local PI. Patients suffering a clinical endpoint (including those included in the primary composite) will remain in the study and should undergo the scheduled follow-ups.

In the case that a patient suffers any clinical endpoint, it is strongly recommended to manage the patients according to Clincal Practice Guidelines. If the physician feels appropriate to initiate or to stop SGLT-2 inhibitor therapy, this will always prevail. Crossover will be annotated and patients followed-up according to original plan.

In all cases, cardiologists from the research team will be available anytime for discussion about the management of patients.

DATA COLLECTION and STUDY PROCEDURES

STUDY EVALUATIONS / TESTS

DapaTAVI is a pragmatic open label randomized clinical trial. There are no medical specific procedures apart from telephone follow ups and registries consultation. No medical exams or tests will be performed for the study matter. All exams and actions are those clinically indicated and the study investigators will collect data from clinical records.

DATA RECORDING

The following variables will be collected and included in the web-based eCRD.

BASELINE VARIABLES TO COLLECT			
Number	Variable		
Demographic and antropometric data			
1	Age		
2	Sex		
3	Weight		
4	Height		
Cardiovascular risk factors			
5	Hypertension		
6	Diabetes mellitus		
Cardiovascular history			
8	Peripheral artery disease		
9	Ischemic heart disease		
10	Prior myocardial infarction		
11	Prior stroke		
12	Atrial fibrillation		
13	Bundle branch block prior to TAVI		
14	Prior pacemaker		
15	Prior aortic bioprothesis		
16	Prior valvuloplasthy		
Comorbidity			
17	Chronic obstructive pulmonary disease		
18	Chronic kidney disease		
Echocardiographic data (prior to TAVI)			
19	Left ventricular ejection fraction		

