Researchers will be offered with the possibility of completing baseline variables by the coordinating center (University Hospital Álvaro Cunqueiro, Vigo, Spain). For this purpose, a copy of the admission report will be requested. To comply with the protection data law, the admission reports should be sent in a secure system.

When accessing via website, there will an option for "upload admission report". The file containing the report (.pdf or .doc) will be selected and uploaded in the system. Since the variables collected in DapaTAVI are those clinically available, it is expected that most of the information will be contained in the admission report.

When accessing via mobile app, there will a possibility of taking a photograph of the admission report with the mobile camera. To avoid retention of photos of the admission report in the mobile phones, the app will not allow selection of previously done photos, only a direct access to the camera via app.

FOLLOW-UP PROCEDURES

• Specific study follow-up. All patients will be monitored by telephone and through their medical records at 3±1 and 12 months, to know their vital status, development of an end-point event or any adverse effect. Whenever a patient presents a clinical event, the medical history will be requested to the local PI. For the DapaTAVI trial, no specific ECG, echocardiogram, or laboratory monitoring are need, only clinical data.

Local researchers will be offered with the possibility of doing telephone calls from the national coordinating center (Hospital Álvaro Cunqueiro, Vigo, Spain). This will be agreed at the beginning of the study or anytime during the march of the trial (i.e. if a center initially is willing to do telephone follow-ups but later thinks this is not possible, the coordinating center will take over this responsibility anytime).

On phone calls, the following fields will be completed after interacting with the patient/family:

- 1. Vital status (alive/death). If death, cause of death (cardiovascular, non-cardiovascular).
- 2. Any HF hospital readmissions or visit to the emergency department (yes/no).

When the patient died or was admitted to a hospital for any cause which may be related to any of the study endpoints, medical reports will be requested to the local investigator.

- 3. Adherence to randomization arm (yes/no). If no, date (month/year) of crossover, and reason for crossover (free text field).
- 4. Functional health status by the NYHA scale.

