Randomization introduces a deliberate element of chance into the assignment of treatments to subjects in a clinical trial. In this trial, randomization procedure is organized centrally, and it is characterized by being stratified by center and follows a permuted-block design with varying block sizes to reduce predictability of the random sequence.

Blinding:

As this trial follows a PROBE design, open-label and blinded endpoint adjudication are intrinsic characteristics. Masking is no implemented for patient and care provider. Therefore, to reduce potential bias, the endpoint adjudication panel remains blinded to treatment allocation and hard clinical meaningful endpoints have been selected as primary endpoint.

• Multiplicity:

Multiplicity can raise concerns regarding type I error. To address multiplicity problems, two strategies are implemented. First, a composite endpoint is selected as primary endpoint. Second, Haybittle-Peto approach is applied to account for interim analyses.

• External validity:

The pragmatic design of this trial, as evaluated through PRECIS-2 guidelines, increases the generalizability of its conclusions to real daily clinical practice.

DESCRIPTIVE ANALYSIS

The distribution of continuous variables will be analyzed with graphical methods. For normally distributed variables, results will be expressed as mean \pm SD; otherwise they will be represented as median (first quartile to third quartile). Categorical variables will be expressed as absolute frequency (%). Significance testing of baseline differences between treatment groups will be not performed.

PRIMARY ANALYSIS

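### The orthostatic limb of the symptomatic-hypotension safety endpoint requires neither a symptom nor new onset, so it can mask a true difference or, if detection is unequal, create a false one

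*Combined protocol and SAP*

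**What the plan says.** The synopsis lists the tertiary safety outcomes as "endpoints (incidence rate of Major hypoglycemia, Symptomatic hypotension" and others, so hypotension is to be reported as an incidence rate by arm. The definition is under Study Endpoints, Tertiary Endpoints: "Symptomatic hypotension includes postural dizziness with systolic blood pressure < 100 mmHg, and orthostatic hypotension (defined as a decrease of >20 mmHg" systolic, with the alternative "pressure or >10 mmHg in diastolic blood pressure from a supine to a standing position". The first limb joins a symptom to a resting pressure. The second gives a complete definition made only of a postural change in pressure.

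The section on definitions of follow-up events does not return to hypotension.

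On measurement, Study Evaluations / Tests states "No medical exams or tests will be performed for the study matter", and Follow-up Procedures states "All patients will be monitored by telephone and through their medical records at 3±1 and 12 months". The numbered call fields cover vital status, heart-failure readmission or emergency visit, adherence and NYHA class. The list of baseline variables, as it stands in the text, contains no blood pressure, lying or standing. The only pressure condition at entry is the exclusion "Systolic blood pressure < 100 mmHg or diastolic blood pressure < 50 mmHg".

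On blinding, Reducing Bias states "Masking is no implemented for patient and care provider", and Event Adjudication states "All events need to be adjudicated by the Clinical Events Adjudication Committee (CEAC").

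**The concern.** The label and the rule do not match. A patient who feels well but whose pressure falls on standing is counted under a heading that says symptomatic. So is a patient who had the same fall before randomisation, because no postural reading is listed at baseline against which to judge it.

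The protocol does better elsewhere. Major hypoglycaemia, in the same list, requires symptoms and requires all of its criteria to be met. A heart-failure admission requires symptoms that are new or worsening.

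A mixed endpoint blurs the safety comparison. The trial orders no lying and standing measurement, so the second limb is met only when a treating clinician, who knows the arm, chooses to take one. The published rate, and the safety data that the DSMB sees at the interim analyses, would then combine symptomatic events with an incidental sign. A reader could not tell in which direction the comparison had been moved.

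**Working it through.** **The plan's own figures.** The documents give no rate, power or sample size for hypotension. The stated sample size rests on the primary endpoint alone and reproduces:

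- Events needed for HR 0.70, two-sided 0.05, power 0.80 (Schoenfeld): 247.
- 247 / 0.255 = 968.6, rounded up to 969; 969 / 0.95 = 1,020, as stated.
- 1,020 × 0.255 = 260.1, matching the stated 260 expected events.

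None of this involves hypotension, so none of it changes.

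**Illustration 1: equal recording in both arms, true drug effect.** Inputs, all assumed: p = risk of a truly symptomatic event; b = risk of a recorded asymptomatic or pre-existing fall, the same in each arm and independent of p. The observed risk is q = 1 − (1 − p)(1 − b).

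Take p = 5% (control) and 10% (dapagliflozin), a true ratio of 2.0. At b = 10%:

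- Control: 1 − 0.95 × 0.90 = 14.5%.
- Dapagliflozin: 1 − 0.90 × 0.90 = 19.0%.
- Ratio: 0.190 / 0.145 = 1.31.

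The power column is for a two-sided 5% comparison of two proportions with 510 per arm. It only gauges lost information, since the plan analyses safety descriptively with confidence intervals.

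| b | control | dapagliflozin | observed ratio | power |
|---|---|---|---|---|
| 0 | 5.0% | 10.0% | 2.00 | 0.86 |
| 5% | 9.75% | 14.5% | 1.49 | 0.64 |
| 10% | 14.5% | 19.0% | 1.31 | 0.49 |
| 20% | 24.0% | 28.0% | 1.17 | 0.31 |

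With p = 3% and 6%, the ratio of 2.0 becomes 1.36, 1.21 and 1.11 at the same three non-zero backgrounds.

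**Illustration 2: no drug effect.** Inputs, all assumed: p = 3% in both arms; b is now the prevalence of an asymptomatic fall; c is the share of such falls that gets measured and recorded. The observed risk is q = 1 − 0.97 × (1 − b × c).

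At b = 10%:

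- c = 30%: 1 − 0.97 × 0.970 = 5.91%.
- c = 45%: 1 − 0.97 × 0.955 = 7.37%.
- c = 60%: 1 − 0.97 × 0.940 = 8.82%.

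The table holds control detection at 30% and varies detection on dapagliflozin.

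| b | equal (30%) | 45% | 60% |
|---|---|---|---|
| 5% | 1.00 | 1.16 | 1.33 |
| 10% | 1.00 | 1.25 | 1.49 |
| 20% | 1.00 | 1.33 | 1.66 |

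The excess comes wholly from the gap in detection. The loose definition is what lets that gap reach the endpoint.

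**The case against.** The strongest reply is that the definition applies to both arms of a randomised trial, so pre-existing falls are balanced in expectation. That stands. A reader might infer from the wording that asymptomatic falls will be counted as drug harm. The documents do not support this: under equal detection the extra events move the ratio towards 1, and an excess on dapagliflozin needs unequal measurement. Open-label care makes unequal measurement plausible, but nothing in the documents shows it.

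A reader might also infer that symptomatic events without a postural element, such as syncope with low seated pressure, are excluded. That does not follow. The protocol says the endpoint includes two presentations, which is not closed wording, whereas it does close the definition of major hypoglycaemia.

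The heading, and the use of incidence, can be read as implying symptoms and newness. This makes the text ambiguous rather than plainly wrong. But sites and adjudicators could then apply different rules, which is itself a reason to settle the wording.

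There are partial safeguards. Low resting pressure is an exclusion, a physical examination is scheduled at enrolment, follow-up is meant to pick up endpoint events and adverse effects in general, and adjudicators do not see the arm. None of these records a postural fall before randomisation, and blinded adjudication cannot recover a fall that was never measured. Because no measurement is mandated, few symptom-free falls may be recorded at all, which limits the effect either way.

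**Conclusion.** The point holds in a limited form. As written, the orthostatic limb admits patients with no symptom and patients whose fall predates randomisation, and no later section corrects this. The likely consequence under equal detection is dilution, which can hide a real difference; under unequal detection it is a false excess. The sizes shown (a ratio of 2.0 reduced to between 1.17 and 1.49 at 5% versus 10%, or spurious ratios of 1.16 to 1.66) depend entirely on assumed rates and on independence of the two kinds of event. They are not forecasts. This is one tertiary safety endpoint, analysed descriptively, with no formal safety stopping rule. It is worth correcting because the change is small and the result will be read as drug safety.

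**What to change.** Make the symptom a condition of both limbs: symptoms attributed to low blood pressure, with onset or worsening after randomisation according to the patient or the medical record, together with either pressure criterion as already written. Leave the pressure thresholds unchanged. Ask the same hypotension-symptom question of both arms at the existing 3-month and 12-month calls. List any recorded asymptomatic orthostatic falls separately by arm, outside this endpoint.

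The cost is a revised definition, matching eCRF logic and one more question per call. Fewer events will be counted. Newness would rest on the patient's account or the record, because no postural reading is required at baseline. The change does not remove unblinded ascertainment: symptoms are still reported by patients and clinicians who know the arm. The common question makes the asking uniform, and the separate listing keeps incidental falls visible without mixing them into the endpoint.

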	patients who undergo TAVI in Spain), post-TAVI mortality in the first year is around 10%.
	In the last 2 years, dapagliflozin, a Sodium-Glucose Co-Transporter type 2
	(SGLT-2) inhibitor, has been shown to significantly reduce cardiovascular
	mortality and HF admission rate by 17% in 17,160 patients with DM [Study
	DECLARE-TIMI 38, NEJM 2019], in 26% in 4,744 patients with LVEF \le \(\)
	40% [DAPA-HF Study, NEJM 2019] and in 29% in 4,304 patients with GFR
	between 25 and 75 ml / min / 1.73 m2 [DAPA-CKD study, presented in
	August 2020 at the European congress of cardiology, pending publication].
	The 3 clinical trials also showed a reduction in total mortality (17% and 31%)
	in DAPA-HF and DAPA-CKD, both significant, and 7% in DECLARE-TIMI-
	38, not significant), and in none of them an increased rate of adverse events
	has been seen compared to placebo. Thus, the 3 studies are consistent in
	reducing CV mortality and readmissions for HF, as well as in terms of drug safety.
	In post-TAVI patients, there is no standard medical treatment beyond
	antithrombotic therapy. Based on the 3 previously discussed clinical trials, it is
	proposed to analyze the possible benefit of prescribing dapagliflozin in post-

	TAVI patients, with a previous history of HF, who have any of these 3
	conditions in which dapagliflozin has shown prognostic benefit: ventricular
	dysfunction (LVEF ≤ 40%), renal dysfunction (GFR 25-75 ml / min / 1.73 m2)
	or DM.
	On the basis that dapagliflozin is a licensed drug, the use of dapagliflozin in
	the present study is supported by 3 published clinical trials with evidence of its
	efficacy (reduction in mortality and HF) and safety (adverse event rate equal
	to placebo), and that the DapaTAVI trial does not require the performance of
	any additional diagnostic or therapeutic test beyond randomization to
	dapagliflozin (yes / no), without any additional risk or burden for patients,
	being a clinical trial independent of the pharmaceutical industry, without no
	commercial interest, it is considered as a low level of intervention.
Study Duration	3 years.
	Recruitment: 2 years
	• Follow-up: 1 year.
Endpoints	Primary endpoint: Incidence rate of the composite of death or worsening
Znapomis	heart failure (HF; including hospitalization for HF or an urgent visit resulting
	in intravenous therapy for HF)
	Secondary endpoints: 1) Incidence rate of individual components of the
	primary outcome. 2) Incidence rate of cardiovascular (CV) mortality. 3)

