> Assumptions:

- Overall alpha value: 0.05
 - o Haybittle-Peto approach for interim monitoring
 - 1st interim analysis: alpha value of 0.001
 - 2nd interim analysis: alpha value of 0.001
 - Final analysis: alpha value of 0.05
- Power: 0.80.
- Test: log-rank (superiority two-sided)
- Minimal treatment effect: HR 0.70.
- 1-year incidence of primary endpoint (controls): 30%
- Accrual period: 2 years
- Follow-up period: 1 year for all patients.
- Percentage of subjects anticipated to withdraw: 5%
- Number of expected primary endpoints: 260.
- > Sample size: 1,020 participants

ADAPTIVE SAMPLE SIZE: The sample size for this study was based on the anticipated incidence of the composite endpoint. It is anticipated that the 1-year incidence of the primary endpoint will be 30% in the control arm and 21% in the dapagliflozin arm (thus, 25.5% in the overall population). To reduce the chances of having an underpowered study secondary to an event rate lower than predicted, a blinded examination of the study overall event rate will be done 3 months before closing the recruitment. At that moment, it is anticipated that >400 patients already underwent 12 months follow-up. In the case that the overall event rate is below 25%, the DSMB will discuss the possibility to doing a re-calculation of sample size according to actual event rate, and the chair will decide if it is needed to increase sample size (thus

extend recruitment period). As this analysis will be performed in a blinded fashion, adjustment for multiplicity is not required and will not be applied.

INTERIM ANALYSIS

Two interim analyses will be performed on primary endpoint and secondary safety endpoints when 33% (86) and 66% (172) of events have been adjudicated. Efficacy and safety interim analyses will be performed following the same methodological guidelines described in this document for the final analysis. Stopping rules for efficacy analysis will be based on the statistical Haybittle-Peto approach, with an overall alpha value 0.05. Safety analyses will be addressed by applying descriptive statistical methods to the data, supplemented by calculation of confidence intervals. No formal statistical stopping rules for safety data will be predefined.

REDUCING BIAS

• Randomization:

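### Genital and urinary infections share one safety endpoint with no planned split, so a rise confined to genital infection could be hard to see (minor).

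*Combined protocol and SAP*

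**What the plan says.** Under Study Endpoints, Tertiary Endpoints, the safety list has one bullet for both infection types: "Genital or Urinary Infections". The Protocol Synopsis (Endpoints) also runs them together, in the string "Genito-urinary infections, Ketoacidosis, Amputation". The section Definitions and Event Adjudication defines neither infection. No section gives a counting rule, an eCRF field or a table layout for the item.

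The Interim Analysis section sets the method: "Safety analyses will be addressed by applying descriptive statistical methods to the data, supplemented by calculation of confidence intervals". It adds: "No formal statistical stopping rules for safety data will be predefined".

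Three other places bear on the point:

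- Under Secondary Endpoints, the components of the primary composite are endpoints in their own right. The infection composite has no such breakdown.
- Under Follow-up Procedures, the telephone fields cover vital status, heart failure readmission or emergency visit, adherence and NYHA class. None is for infection. The same section does say that follow-up is meant to pick up any adverse effect, and the Study Schedule has an adverse events row.
- In the synopsis, the summary of the three supporting trials says that "in none of them an increased rate of adverse events" was seen compared with placebo. No genital or urinary infection rate appears anywhere.

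**The concern.** A composite safety line shows that something moved, but not what. If one component is common and equal in the two arms while the other is rare and raised by treatment, the common one adds noise and pulls the ratio towards 1.

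Safety is to be read from descriptive tables with confidence intervals, without a formal boundary. What the DSMB and later readers see therefore depends on how the rows are drawn. A combined row could read as no clear difference while one component is several times more frequent on dapagliflozin. It could not tell clinicians which infection is involved. The rationale section says that SGLT-2 inhibitors have not been studied in TAVI patients, so tolerability by infection type would be useful output from this trial.

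**Working it through.** **Inputs from the documents.** Allocation is 1:1 with 1,020 patients, so n = 510 per arm. Two-sided alpha is 0.05. Safety is reported with confidence intervals. The plan gives no rate, power or sample size for infections, so it has no infection figure to reproduce. Its overall N does reproduce: 4 × (1.960 + 0.842)² / (ln 0.70)² = 247 events; 247 / 0.255 = 969; 969 / 0.95 = 1,020.

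**Inputs that are assumptions.** Genital infection is 0.5% in control and 2% or 3% on dapagliflozin. Urinary infection (u) is the same in both arms, at 2%, 5%, 8% or 12%.

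**Formulas.** Merged risk = u + genital risk, taking overlap as negligible. Risk difference d = p1 − p0. Wald 95% CI = d ± 1.96 × √[p0(1 − p0)/n + p1(1 − p1)/n]. Power is the exact probability, over two binomials, that the uncorrected chi-square test gives p < 0.05. It serves here only as a gauge of how often the data would show a difference.

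**Worked case, u = 8%, genital 0.5% vs 2%.**

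- Genital alone: ratio 0.020/0.005 = 4.0; d = 1.5 points; SE 0.69 points; CI 0.1 to 2.9.
- Merged: 8.5% vs 10.0%; ratio 0.100/0.085 = 1.18; d = 1.5 points; SE 1.81 points; CI −2.1 to 5.1.

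The absolute excess is the same, but the standard error is about 2.6 times as large (1.81/0.69). If overlap is allowed for, merged risk = 1 − (1 − u)(1 − genital). That gives 8.46% vs 9.84%, a difference of 1.4 points, so little changes.

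**Power with 510 per arm.**

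| Row reported | Genital 0.5% vs 2% | Genital 0.5% vs 3% |
|---|---|---|
| Genital alone | 0.58 | 0.90 |
| Merged, u = 2% | 0.27 | 0.56 |
| Merged, u = 5% | 0.16 | 0.35 |
| Merged, u = 8% | 0.13 | 0.27 |
| Merged, u = 12% | 0.11 | 0.21 |

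Fisher's exact test gives lower values for genital alone (0.49 and 0.86). With 485 per arm (510 × 0.95, after the plan's 5% withdrawal) the chi-square values are 0.56 and 0.88.

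**Both types rise.** Take urinary 5% vs 8% and genital 0.5% vs 1.5%. The merged rates are 5.5% vs 9.5%, with power 0.68. Reported separately, power is 0.49 (urinary) and 0.34 (genital). Here the combined line is the better detector.

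**Early interim look.** Assume a third of the patients' information, 510/3 = 170 per arm. Expected genital infections are 170 × 0.005 = 0.9 vs 170 × 0.02 = 3.4 to 170 × 0.03 = 5.1. Power for genital alone is 0.21-0.43.

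**The case against.** The case against is substantial, and most of it stands.

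- **A single bullet is not a rule to merge.** The text leaves a split unspecified but does not forbid one. That stands. The point is only that no separate comparison is planned.
- **Genital infections would not be invisible.** A reader might infer that they would go unseen apart from Fournier's gangrene. The documents do not support that. Adverse effects are sought at both follow-ups, the Data Handling section has adverse events and expected adverse reactions entered, and crossovers are recorded with reasons. None of this gives a planned comparison by arm, and that gap remains.
- **The differential effect has no source in the documents.** The rationale mentions glucosuric effects only when arguing for benefit in heart failure. The supporting trials are described as showing no increase in adverse events. This stands, so the concern is conditional.
- **The exclusion for recurrent urinary infection might seem to show that the plan itself treats the two types differently.** It does not. An eligibility rule says nothing about tabulation, and by lowering the urinary background it weakens the masking.
- **Merging can help.** It does when both types rise, as shown above. This is a reason to keep the combined line, but not to report it alone.
- **Power is a secondary yardstick.** Safety is descriptive, and the absolute difference survives merging. True, but the interval and the ratio are what a descriptive table is read from, and both are affected.

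**Conclusion.** The point holds as a minor one. The plan names one combined infection endpoint and schedules no separate reporting. If urinary infection is similar in the two arms and genital infection is rarer but raised, the combined row loses much of its ability to show the rise. Under the assumed 0.5% vs 2-3%, power falls from 0.58-0.90 to 0.27-0.56 with a 2% urinary background and to 0.11-0.21 with 12%. These sizes rest wholly on assumed rates, equal urinary risk in both arms and complete capture in 510 patients per arm.

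A reader might infer that the plan will conceal a known harm, or that the DSMB would be misled at its first look. Neither follows. The documents do not state that genital infection is raised, and so few events are expected early that a separate row adds little then. The gain is mainly at the final analysis. The endpoint is tertiary, and the primary analysis and sample size are unaffected.

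**What to change.** 1. In the Protocol Synopsis and under Tertiary Endpoints, replace the combined item with two safety endpoints, genital infection and urinary tract infection, and define each in the definitions section.
2. Give each its own field in the eCRF and in the telephone follow-up list, which at present has no infection item.
3. Report counts, risk difference and 95% CI by arm for each, and keep the combined rate alongside.

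The cost is two data fields, two short definitions and an extra table row. No visit, test or sample size changes. The downside is one more descriptive safety comparison, to be read with the others and without a formal test.
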